3.2. Primary Safety Endpoints

The safety of Envarsus treatment will be assessed by: The timing and incidence of study defined Grade 3 or higher infection

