9.4. Visit Time Frames/ Windows

Study visits should take place within the time frames specified below in Table 1. The designated visit windows for each scheduled study visit are indicated in Appendix 1 Schedule of Events.

Visit No.	Study Visit Label	Time Frame Post Transplant
Screen	Study Eligibility	Approximately 1 month
1	Enrollment Day 0/ Visit 1	Approximately 2 months
2	Study Day 30/ Visit 2	Approximately 3 months
3	Study Day 120/ Visit 3	Approximately 6 months
4	Study Day 210/ Visit 4	Approximately 9 months
5	Study Day 300/ Visit 5	Approximately 12 months

10. Criteria for Participant Completion and Premature Study Termination

Participants may be prematurely terminated from the study for the following reasons:

- The participant elects to withdraw consent from all future study activities, including follow-up.
- The participant is "lost to follow-up" 3 months after the date of a missed study visit (i.e., no further follow-up is possible because attempts to reestablish contact with the participant have failed).
- The participant dies.
- The Investigator no longer believes participation is in the best interest of the participant.
- CTCAE Grade 3 or higher drug-related reaction
- A decision is made by the investigators and/or study supporter to stop the study

11. Safety Monitoring and Reporting

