11.4. Collection and Recording of Adverse Events 11.4.1. Collection Period

Adverse events will be collected from the time of first study mandated activity

until a subject completes study participation or until 30 days after he/she prematurely withdraws (without withdrawing consent), or is withdrawn from the study.

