11.7. Reporting of Other Safety Information

An investigator shall notify the site IRB according to the site's IRB guidelines when an "unanticipated problem involving risks to participants or others" is identified, which is not otherwise reportable as an adverse event.

12. Statistical Considerations and Analytical Plan

This is a single center prospective study comparing incidence of BK infection in rapid metabolizers converted from tacrolimus to Envarsus against a recent historical control of rapidly metabolizing recipients who had BK screening at similar points, but remained on tacrolimus.

This study has both safety and efficacy endpoints.

We will use standard descriptive statistics for continuous and categorical data to define adverse events, and clinical outcomes as noted above. Analysis will be undertaken utilizing UAB statistical support in the School of Public Health and Transplant Quality, Informatics and Outcomes.

The enrollment plan is based on a power calculation. A population of 100 patients is calculated

to show significant difference for p value < 0.05.

Our results will be submitted to national/international nephrology/transplant meetings, and as a primary manuscript reporting the primary efficacy and safety data, and secondary manuscripts reporting different secondary endpoints, as appropriate.

We expect the changes over time in these assays to be approximately linear. If after examination of the data, this appears to not be the case, then we will either transform the assay measures or model the time axis time points as an unordered factor (similar to repeated measures ANOVA, but without the requirement for fully balanced data).

We will use descriptive analyses to summarize subject characteristics of our study population. Dichotomous variables will be summarized as proportions with 95% confidence intervals. Continuous variables will be summarized using means, standard deviations, and 95% confidence intervals if they are symmetric and unimodal. Otherwise, they will be summarized using the median and the interquartile range. Simple t-, chi-squared, or Fisher's exact test, as appropriate, will be used to compare quantitative measures across treatment groups. The following variables will be summarized:

- Baseline and demographic characteristics
- Use of concomitant medications
- Reasons for early termination
- All reportable AEs

No formal interim analyses of this study are planned.

13. Identification and Access to Source Data

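### The primary safety endpoint names timing and incidence of Grade 3 or higher infection, but no method in Section 12 accounts for unequal follow-up or censoring

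*Combined protocol and SAP*

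**What the plan says.** Section 3.2 defines the primary safety endpoint as "The timing and incidence of study defined Grade 3 or higher infection". It has two components, whether such an infection occurs and when. Section 11.3.1 supplies the grading scale, on which death from infection is Grade 5.

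The methods are all in Section 12. For adverse events and outcomes: "We will use standard descriptive statistics for continuous and categorical data to define adverse events, and clinical outcomes as noted above". For yes/no variables: "Dichotomous variables will be summarized as proportions with 95% confidence intervals". For continuous variables: "Continuous variables will be summarized using means, standard deviations, and 95% confidence intervals if they are symmetric and unimodal", with median and interquartile range otherwise. For comparisons: "Simple t-, chi-squared, or Fisher's exact test, as appropriate, will be used to compare quantitative measures across treatment groups". The only text on change over time is "We expect the changes over time in these assays to be approximately linear", which concerns assay measures and not time to an event.

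Planned follow-up is 300 days from enrollment (Sections 9.2 and 9.4). It can be cut short. Section 10 begins "Participants may be prematurely terminated from the study for the following reasons" and lists consent withdrawal, loss to follow-up, death, investigator judgement, a Grade 3 or higher drug-related reaction, and a decision to stop the study. On collection, Section 11.4.1 says "Adverse events will be collected from the time of first study mandated activity"; it ends at completion, or 30 days after a withdrawal that does not withdraw consent.

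**The concern.** Section 12 is readable and complete on this point, yet it contains no cumulative incidence or Kaplan-Meier estimate, person-time rate, censoring rule or competing-event rule. Two things follow.

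First, incidence reported as a proportion needs a denominator, and the plan does not say how patients with partial follow-up enter it. The answer decides whether the estimate is too low or too high.

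Second, under the listed methods a time value exists only for patients who become infected. A mean or median of those values leaves out infections that happen after a patient's observation ends. The patients still at risk without an event contribute nothing.

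The origin of the time scale is also open. Collection starts at the first mandated study activity, enrollment is the signing of consent (Section 9.1), and Appendix 1 counts days from randomization although Section 12 describes a comparison with historical controls. At stake is whether the named primary safety endpoint can be read as a risk over a defined period, and whether the choice of denominator could be made after the data are seen.

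**Working it through.** **No figure to reproduce.** The documents give no expected infection rate, no exit rate and no dropout allowance for this study. The 100-patient figure in Sections 3.1 and 12 is not tied to this endpoint.

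**Inputs.**
- From the documents: 300 days of follow-up (Section 9.4) and a 30-day collection tail (Section 11.4.1).
- Assumed: true 300-day risk p = 12%, constant hazard, and exits independent of infection and spread evenly over 300 days.
- Exit fractions e are assumed to be 5.6%, 10% and 20%. The 5.6% adds the 1.5% lost to follow-up and 4.1% deaths at 24 months on Envarsus in the cited de novo trial (Section 2.4.1). It is a rough anchor only: it leaves out consent withdrawal and investigator decisions, and it includes deaths.

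**Step 1. Infections observed among early exits.** L = -ln(1 - 0.12) = 0.127833 over 300 days. The tail is 30/300 = 0.1 of the period.
- With the tail: v = 1 - [(exp(-0.1L) - exp(-L))/L + 0.1 exp(-L)] = 1 - [(0.987298 - 0.88)/0.127833 + 0.088] = 1 - [0.83936 + 0.088] = 0.0726.
- Without the tail: v0 = 1 - 0.12/0.127833 = 0.0613.

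**Step 2. Exits kept in the denominator as non-events.** Crude proportion = (1 - e) × 0.12 + e × v.

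**Step 3. Exits dropped from the denominator but their infections counted.** Divide the Step 2 result with the tail by (1 - e).

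| Exits | Step 2, with tail | Step 2, no tail | Step 3 |
|---|---|---|---|
| 5.6% | 0.1133 + 0.0041 = 11.7% | 11.7% | 0.1173/0.944 = 12.4% |
| 10% | 0.1080 + 0.0073 = 11.5% | 11.4% | 0.1153/0.90 = 12.8% |
| 20% | 0.0960 + 0.0145 = 11.1% | 10.8% | 0.1105/0.80 = 13.8% |

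The true value is 12% throughout. Section 11.4.1 gives no tail to patients who withdraw consent, so the real figure would lie between the two Step 2 columns.

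**Cross-check.** With a true risk of 10%, exits at a constant rate and the tail included, the Step 2 figure is 9.8%, 9.6%, 9.2% and 8.7% at 5%, 10%, 20% and 30% exits. The relative bias is -2%, -4%, -8% and -13%.

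**Scale.** The standard error of a 12% proportion is sqrt(0.12 × 0.88/n), which is 4.6 percentage points at n = 50 and 3.2 at n = 100.

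**Step 4. Timing among infected patients only, complete follow-up.** The mean day of infection is 300 - (integral of F(t) from 0 to 300)/p, where F is the cumulative risk.
- Constant hazard with risks of 5%, 10%, 20% and 40%: mean day 148.7, 147.4, 144.4 and 137.3.
- Risk fixed at 12% with a Weibull hazard: mean day 97 when infections come early (shape 0.5), 147 when the hazard is constant, and 197 when they come late (shape 2).

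The summary hardly responds to the level of risk, which is the job of the incidence component. It does respond to when infections occur.

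**The case against.** The strongest reply is that this is a descriptive endpoint with few events (12% of 50 to 100 patients is 6 to 12), that Section 12 already tabulates reasons for early termination, and that sampling error is far larger than the bias. The figures support the last point. At 5.6% to 20% exits the Step 2 shortfall is about 0.3 to 0.9 points with the tail, against a standard error of 3.2 to 4.6. This limits the importance of the point. It does not supply a denominator, a time origin or a censoring rule.

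Three stronger readings are tempting, and the documents do not support them.

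- A reader might infer that early exits necessarily bias the infection risk downward. That requires them to stay in the denominator as non-events, which the plan does not state. Step 3 shows the opposite direction under another reading. Nor does every exit cause bias: a patient who dies of infection has had the event, and one who dies uninfected of another cause is a non-event once death is treated as competing. A Grade 3 or higher drug-related reaction may itself be the infection.
- A reader might infer from the near-constant mean day that the listed methods cannot deliver timing at all. That constancy comes from assuming a constant hazard. Step 4 shows the mean moving by about 100 days when the shape of the hazard changes.
- A reader might infer that Envarsus will look safer than the controls, because Section 3.1 requires controls to have BK data through month 12. The documents do not say whether Grade 3 or higher infections are collected for controls, so a between-group bias cannot be claimed.

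**Conclusion.** The concern holds as a mismatch between endpoint and method. The primary safety endpoint has a time component and will be observed over unequal follow-up, yet no stated method uses follow-up time or censoring. This does not depend on the exit rate.

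The numerical effect is modest, and its direction depends on an unstated choice. For a true 12%, the crude figure is 11.7% to 11.1% if exits count as non-events and 12.4% to 13.8% if they are dropped while their infections are kept, over 5.6% to 20% exits. These values rest on an assumed risk, a constant hazard and independent exits. Exits linked to toxicity could change the size. A timing summary among infected patients is informative but incomplete, because it ignores censoring.

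The change is worth making: it costs little, removes the dependence on the denominator, and reports both parts of the endpoint in one estimate.

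**What to change.** In Section 12, state that the primary safety endpoint is analysed as time from first Envarsus dose to first study-defined Grade 3 or higher infection. Report the cumulative incidence curve (Aalen-Johansen) with a 95% confidence interval at day 300. Death not due to infection is a competing event; death from infection is an event. Patients are censored at the end of adverse-event collection under Section 11.4.1. Estimates at days 30, 120 and 210 and a rate per person-time are optional. Because collection starts before the first dose, list any qualifying infection in that interval separately.

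This needs one standard analysis and, if not already captured, the dates of first dose and of infection onset. It changes no visit or treatment rule. The estimate may be slightly less favourable than a crude proportion that counts early exits as infection-free. The estimator assumes that censoring is independent of infection risk, so the planned table of reasons for early termination should be read alongside it.

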3.3. Primary Efficacy Endpoint

The efficacy primary endpoint of the study is the composite of BK Virus Infection, including viruria > 500 copies, viremia > 500 copies, or nephropathy as defined by Banff classification (g/msv 40 positivity with or without tubulitis or if/ta).

3.4. Secondary Efficacy Endpoints

The secondary end-points to evaluate the effect of Envarsus conversion will

include: incidence of rejection, graft failure, graft dysfunction as defined by a 15% decrease in estimated glomerular filtration rate (eGFR), and proteinuria.

4. Rationale for Study Population

4.1. Enrollment Eligibility Criteria

4.1.1. Inclusion Criteria

Individuals who meet all of the following criteria are eligible for enrollment as study participants:

- 1. Patient must be able to understand and provide informed consent
- 2. Age \geq 18 years of age at the time of study entry
- 3. Recipient of a deceased or living donor kidney transplantation
- Maintenance immunosuppression consisting of tacrolimus/MMF/MPA (≥1000 mg/720 mg daily) ± prednisone (≤10 mg/day)
- 5. Patient is less than or at 8 weeks post transplant with a negative serum BK Virus screen at 3-4 weeks post transplant
- 6. Patient has a tacrolimus drug dose/concentration of > 1 with therapeutic tacrolimus levels.
- 7. Women of childbearing potential defined as all women physiologically capable of becoming pregnant, must have reviewed Mycophenolate REMS and have a negative pregnancy test upon study entry.
- 8. Female (and male) subjects with reproductive potential must agree to use a highly effective method of birth control for the duration of the study. Please note that according to the US product information for MMF/MPA, two reliable forms of contraception must be used simultaneously unless female sterilization, male sterilization, post-menopausal status or total abstinence is the chosen method.

Acceptable methods of highly effective birth control include:

- Condom with spermicide
- Diaphragm and sperm ide
- Cervical cap and spermicide
- Use of oral, injected or implanted hormonal methods of contraception or other forms of hormonal contraception that have comparable efficacy (failure rate <1%), for example hormone vaginal ring or transdermal hormone contraction
- Intrauterine device (IUD)

Female sterilization (have had surgical bilateral oophorectomy with or without hysterectomy) or tubal ligation at least six weeks prior to screening.

Male sterilization at least 6 months prior to screening. For female subjects on the study, the vasectomized male partner should be the sole partner for that subject.

Post menopausal women defined as being not of child bearing potential if they have had 12 months of natural (spontaneous) amenorrhea.

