2.1. Background and Scientific Rationale

2.1.1. BK Viral Infection

Development of BK Infection post transplant is largely attributed to reactivation of virus in the donor allograft. Risk factors are multifactorial and can not be linked to an individual immunosuppression agent. Degree of immunosuppression is the most consistent risk factor, and reduction of immunosuppression is the most effective treatment. Rates of BK viruria, viremia, and nephropathy are 40%, 20%, and 1-10% respectively^{10,19}. BK virus nephropathy (BKVN) is strongly and independently associated with poor graft survival. BKVN has a high graft failure rate at over 50%. Peak incidence of BK infection is in the first year post transplant.

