3.1. Description of Study Design

This will be a single center prospective case control study. We expect 40% of patients will develop BK viruria, 20% BK viremia, 5% BK viral nephropathy (BKVN). Patients will be managed using standard of care for our center (thymoglobulin induction, tacrolimus/mycophenolate/prednisone). Target tacrolimus level is 8-12 ng/mL for the first 6 months post transplant and 6-9 ng/mL thereafter. BK urine/serum is routinely monitored during the first year post transplant. A population of 100 patients is calculated to show significant difference for p value < 0.05.

Population:

Study Group: Post transplant patients (kidney transplant alone) with standard of care immunosuppression, no prior rejection, prior BK or opportunistic infection, and negative BK screening at post-transplant month 1, who have a tacrolimus concentration/dose of < 1 and a steady state therapeutic level will be eligible. Patients who consent to participate will be converted to Envarsus at 20% reduction in tacrolimus dose.

Control Group: Post transplant patients (kidney transplant alone performed between 10-2016 and time of consideration for study control group) with standard of care immunosuppression, no prior rejection, prior BK or opportunistic infection, who had a negative BK screening at post-transplant month 1 and tacrolimus concentration/dose of < 1 at post-transplant month 1, and BK data available for months 2, 3, 6, 9, 12 post transplant.

Study visits: Post-transplant Months 2, 3, 6, 9, 12

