4.1.2 Exclusion Criteria

Individuals who meet any of these criteria are not eligible for enrollment as study participants:

- 1. Inability or unwillingness of a patient to give written informed consent or comply with study protocol
- 2. History of graft loss from acute rejection within 1 year after any previous kidney transplant
- 3. History of previous liver, heart, pancreas, or lung transplant
- 4. History of cellular rejection of current allograft prior to enrollment
- 5. Serum BK virus ≥500 copies/mL by PCR at the time of study entry
- 6. Female subjects who are pregnant or breast feeding
- 7. Participation in any other studies with investigational drugs or regimens in the preceding year from the time of study entry
- 8. Any condition or prior treatment which, in the opinion of the investigator, precludes study participation
- 9. Patients requiring the use of azathioprine or mTOR inhibitors
- 10. Patients with active peptic ulcer disease

5. Investigational Agent: Envarsus

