6.1.2 Mycophenolate Mofetil (MMF)/ Mycophenolic Acid (MPA)

All enrolled subjects will be on MMF/MPA at the time of study entry at a minimum dose of 1000 mg/720 mg per day. Once subjects are enrolled in the study, doses may be adjusted at the discretion of the study investigator for gastrointestinal intolerance, cytopenias, infections or other conditions that require dose adjustment. All mycophenolate prescribers in the study will be required to enroll in the FDA mycophenolate REMS (risk evaluation and mitigation strategy) program.

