9.1. Enrollment

The research study will be explained in lay terms to each potential research participant. The potential participant will sign an informed consent form before undergoing any study procedures. A participant is considered enrolled in the trial once the consent form has been signed.

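### The mycophenolate minimum and prednisone ceiling at entry are not carried to the historical controls, so comparable baseline immunosuppression is not assured

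*Combined protocol and SAP*

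**What the plan says.** **Envarsus group.** The numbered criteria in 4.1.1 govern entry to the trial: "Individuals who meet all of the following criteria are eligible for enrollment as study participants". Item 4 requires "Maintenance immunosuppression consisting of tacrolimus/MMF/MPA (≥1000 mg/720 mg daily) ± prednisone (≤10 mg/day". Section 6.1.2 repeats the mycophenolate part: "All enrolled subjects will be on MMF/MPA at the time of study entry at a minimum dose of 1000 mg/720 mg per day". It then allows later dose changes. Item 5 lets entry occur up to 8 weeks after transplant. Section 9.1 defines enrollment by consent: "A participant is considered enrolled in the trial once the consent form has been signed". Section 3.1 mentions consent only for the group converted to Envarsus.

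**Control group.** Section 3.1 gives a separate list for historical patients: kidney transplant alone, standard-of-care immunosuppression, no prior rejection, BK or opportunistic infection, a negative BK screen and a concentration/dose ratio below 1 at month 1, and BK data at months 2, 3, 6, 9 and 12. It contains no mycophenolate minimum and no prednisone ceiling, and nothing applies section 4.1 to these patients.

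**Standard of care.** Section 3.1 describes it as "standard of care for our center (thymoglobulin induction, tacrolimus/mycophenolate/prednisone", with no mycophenolate or prednisone dose. The same phrase binds the other arm: "Study Group: Post transplant patients (kidney transplant alone) with standard of care immunosuppression". Section 6.1.3 counts corticosteroids as part of the trial regimen.

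**Why dose matters here.** Section 2.1.1 states: "Degree of immunosuppression is the most consistent risk factor".

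**Analysis.** Section 12 names t, chi-squared or Fisher's exact tests across groups, and summaries of baseline characteristics and concomitant medications. It states no matching and no covariate adjustment.

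**The concern.** In a non-randomized comparison with a historical control, identical eligibility is the main protection against selection bias. Here one group must satisfy dose limits at entry and the other need not, and the limits concern the factor that the protocol ranks first for BK infection. A historical patient on mycophenolate below the minimum, or on prednisone above the ceiling, fits the control list but would be refused for the Envarsus group.

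The assessment dates widen the gap. Controls qualify at month 1, while Envarsus patients must meet item 4 when they enter, which can be up to 8 weeks after transplant. Someone whose mycophenolate falls below the minimum between those dates remains a control but cannot enter the Envarsus group.

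At stake is whether a difference in the BK composite can be read as an effect of conversion rather than of who was admitted to each group.

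**Working it through.** **1. The two definitions side by side**

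| Feature | Envarsus group | Historical controls |
|---|---|---|
| Governing text | 4.1.1, 4.1.2 and 3.1 | 3.1 only |
| General regimen | Standard of care (3.1) | Standard of care (3.1) |
| Mycophenolate minimum | MMF 1000 mg / MPA 720 mg daily (item 4, 6.1.2) | None stated |
| Prednisone ceiling | 10 mg/day (item 4) | None stated |
| Prednisone required? | Optional in item 4; part of the regimen in 3.1 and 6.1.3 | Part of the regimen in 3.1 |
| When assessed | Entry, up to 8 weeks | Month 1 |
| Adjustment for dose | None stated (section 12) | None stated (section 12) |

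The two numeric limits and the assessment date differ between groups. The prednisone-required row is different in kind: item 4 disagrees with 3.1 and 6.1.3 about the Envarsus group itself.

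**2. The plan's own figure**

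Sections 3.1 and 12 give 100 patients at p < 0.05. Effect size, power, sidedness and allocation are not stated, so the figure can be neither reproduced nor refuted, and this point does not turn on it. For scale only: with 50 per group, two-sided 0.05 and 40% in controls (the viruria rate in 3.1), 80% power needs an Envarsus rate of about 15%, a difference of about 25 points. At 40% against 20% the power is 59%.

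**3. Illustrative size of the bias**

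Assumptions: 50 per group; no true Envarsus effect; BK risk p = 0.40 in everyone within the item 4 limits; a share x of controls outside them with relative risk r. The documents give neither x nor r.

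- Control rate: p_c = p[(1 − x) + x·r]
- Spurious difference (control minus Envarsus): p·x·(r − 1)

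For x = 0.2 and r = 1.5, p_c = 0.40 × (0.8 + 0.3) = 0.44, a difference of 4 points.

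Rejection rate by the normal approximation:
- Pooled SE: √(0.42 × 0.58 × 2/50) = 0.0987
- Unpooled SE: √[(0.44 × 0.56 + 0.40 × 0.60)/50] = 0.0986
- Favoring Envarsus: 1 − Φ[(1.96 × 0.0987 − 0.04)/0.0986] = 6.0%
- Against Envarsus: Φ[(−1.96 × 0.0987 − 0.04)/0.0986] = 0.9%
- Total: 6.9%, against a nominal 5%

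Spurious difference in points, with the two-sided rejection rate in parentheses:

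| Share outside, x | r = 0.5 | r = 1.5 | r = 2.0 |
|---|---|---|---|
| 0.1 | −2 (5.5%) | +2 (5.5%) | +4 (6.9%) |
| 0.2 | −4 (6.9%) | +4 (6.9%) | +8 (12.6%) |
| 0.3 | −6 (9.5%) | +6 (9.3%) | +12 (22.4%) |
| 0.5 | −10 (18.1%) | +10 (17.0%) | +20 (51.6%) |

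A positive value flatters Envarsus. If no control falls outside the limits (x = 0), the bias is nil.

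**4. Direction**

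Controls below the mycophenolate minimum would be expected to lower the control BK rate and work against Envarsus. Controls above the prednisone ceiling would, if total exposure matters as 2.1.1 says, raise it and favor Envarsus. The documents do not say which group is larger.

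**The case against.** The strongest reply is that 3.1 uses the same standard-of-care wording for both groups, at one center, with one named regimen. If routine doses there already satisfy item 4, nothing differs in practice. Controls with prior rejection, BK or opportunistic infection are also excluded, which removes some routes to unusual dosing. The minimum binds Envarsus patients only at entry, so lasting separation of the groups is not shown. Section 12 already summarizes concomitant medications by group.

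Much of this stands, and it rules out several stronger readings that a reader might infer:

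- *The groups are selected to different immunosuppression by design.* The documents show a missing safeguard. They do not show how many controls fall outside the limits.
- *Only Envarsus patients may be steroid-free or lack thymoglobulin.* Section 3.1 holds both groups to the same named regimen. Optional prednisone in item 4 is first an internal contradiction.
- *The exclusion of "Patients requiring the use of azathioprine or mTOR inhibitors" (4.1.2) creates a further imbalance.* This is largely nominal, since a control on such a regimen would not fit the tacrolimus, mycophenolate and prednisone standard.
- *The bias favors Envarsus.* Section 2.1.2 says that studies conflict on steroid-free regimens and on induction, and the two dose limits pull in opposite directions.
- *The age, prior-transplant and investigational-drug criteria add to the problem.* The documents do not link these to BK infection.

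The reply does not close the dose gap. The standard of care is described by drug and not by dose, so a patient can be on it and outside item 4. A summary table can reveal an imbalance but does not correct it. The reasons for mycophenolate reduction in 6.1.2 concern patients after enrollment, so they show only that doses can change, not how often they did among historical patients.

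**Conclusion.** The point holds in a limited form. The item 4 dose limits bind consented Envarsus patients at entry. The control definition carries no such limits and is assessed at an earlier date, and no matching or adjustment is stated. Comparable baseline immunosuppression is therefore not assured. Separately, optional prednisone in item 4 contradicts 3.1 and 6.1.3 and must be reconciled.

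Neither size nor direction can be determined from the documents. Under the assumptions shown, 20% of controls outside the limits gives a spurious difference of 4 points in either direction at relative risks of 1.5 and 0.5, and 8 points at 2.0. Four points is modest beside the roughly 25 points that 50 per group could detect with 80% power. The larger entries in the table need large shares or strong risk differences, for which there is no evidence. This is a weakness that should be repaired because the repair is cheap. It is not a demonstration that the primary comparison is confounded.

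**What to change.** 1. In 3.1, require controls to meet the same item 4 limits as the Envarsus group, read from the chart at a time point matching study entry. Use the dose in force before any change made in response to a BK result at that time point, so that controls are not selected on the outcome.
2. Reconcile item 4 with 3.1 and 6.1.3 so that one steroid and induction rule applies to both groups. Which rule is for the investigators to decide.
3. In section 12, tabulate mycophenolate and prednisone dose at that time point by group.
4. Prespecify a supportive comparison of the primary composite adjusted for those two doses. They are baseline values, so adjustment does not remove any effect of conversion.

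The cost is protocol wording, some chart abstraction and somewhat fewer eligible controls. No recalculated sample size follows from this point.

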1.3. Primary Efficacy Objective

The primary efficacy endpoint of the study is the composite of BK Virus infection, including viruria > 500 copies, viremia > 500 copies, or nephropathy as defined by Banff classification (sv 40 positivity with or without tubulitis or if/ta).

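### Viremia at study entry bars a treated patient, while month 2 viremia in a control can count as an event; the primary composite also has no start date, so Day 0 viruria can be scored

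*Combined protocol and SAP*

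**What the plan says.** **Endpoint.** Section 1.3 states that "The primary efficacy endpoint of the study is the composite of BK Virus infection". Section 3.3 lists its components as "including viruria > 500 copies, viremia > 500 copies, or nephropathy as defined by Banff classification". Neither section, nor section 12, says when counting starts or that a result must be newly positive.

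**Study group.** Section 4.1.1 item 5 allows enrolment up to 8 weeks post transplant "with a negative serum BK Virus screen at 3-4 weeks post transplant". Section 4.1.2 item 5 excludes "Serum BK virus ≥500 copies/mL by PCR at the time of study entry". Section 3.1 adds "no prior rejection, prior BK or opportunistic infection, and negative BK screening at post-transplant month 1" without naming specimen or threshold. It then says "Patients who consent to participate will be converted to Envarsus".

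**Controls.** Section 3.1 asks for no "prior BK or opportunistic infection, who had a negative BK screening at post-transplant month 1", and for "BK data available for months 2, 3, 6, 9, 12 post transplant". No BK condition is stated for controls at month 2.

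**Timing.** Table 1 in 9.4 places Day 0 at about month 2, and 3.1 lists month 2 as a study visit. Appendix 1 schedules urine and serum BK PCR at Screen, Day 0 and every later visit.

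**The concern.** The comparison is with historical controls, so both groups must start at the same point and pass the same entry conditions. They do not.

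1. A patient who becomes viremic between month 1 and month 2 is turned away from the study group. The same patient among the controls stays in and can be scored on the required month 2 result. The error runs one way only, towards Envarsus, and randomisation is not there to remove it.

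2. Month 2 is both the baseline visit and a listed study visit. A urine result above 500 copies on the Day 0 sample meets the endpoint wording, yet conversion on or after Day 0 cannot have prevented it. Viruria is the most frequent component expected (40%, against 20% viremia and 5% nephropathy), so such results would enter the primary result directly.

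**Working it through.** **The plan's own figure.** Sections 3.1 and 12 give 100 patients at p < 0.05, without effect size, power, sidedness or allocation, so the figure cannot be reproduced. Assuming 50 per group, a 40% control rate, a two-sided 5% test and 80% power, it fits an Envarsus rate of about 15% (40% against 15% needs 98 in total). Other inputs would fit as well.

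**The two groups side by side.**

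| | Study group | Controls |
|---|---|---|
| Month 1 BK screen negative | required | required |
| Serum BK below 500 at entry / month 2 | required at entry, up to week 8 | not stated |
| Month 2 result | Day 0 sample, also a listed study visit | required data point |

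The gap in the second row depends on enrolment timing. Near week 4 the entry test almost coincides with the month 1 screen that controls also pass, so the asymmetry is small. Near week 8 it spans about four weeks.

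**Assumptions for the illustrations (not in the documents).** 50 per group; composite risk 40%, borrowed from the viruria rate because no composite rate is given; two-sided uncorrected chi-squared test at 0.05, by exact enumeration. The 40% is read in two ways: as risk on top of what is present at month 2 (A), or as the control total including it (B).

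**Step 1: serum asymmetry, no drug effect, everyone enrolled near month 2.** Let s be the share of controls viremic at month 2.
- A: control = s + (1 − s) × 0.40; Envarsus = 0.40.
- B: control = 0.40; Envarsus = (0.40 − s)/(1 − s).

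| s | A: control vs Envarsus | Apparent RR | Significant for Envarsus | B: control vs Envarsus | Apparent RR | Significant for Envarsus |
|---|---|---|---|---|---|---|
| 0 | 0.400 vs 0.400 | 1.00 | 2.6% | 0.400 vs 0.400 | 1.00 | 2.6% |
| 1% | 0.406 vs 0.400 | 0.99 | 3.0% | 0.400 vs 0.394 | 0.98 | 3.0% |
| 2% | 0.412 vs 0.400 | 0.97 | 3.5% | 0.400 vs 0.388 | 0.97 | 3.4% |
| 5% | 0.430 vs 0.400 | 0.93 | 5.2% | 0.400 vs 0.368 | 0.92 | 5.2% |

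For scale, 2.3.2 reports 8% viremia in total among fast metabolizers, so 5% already at month 2 is a high value.

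**Step 2: Day 0 viruria scored in both groups, true RR 0.5 on later events.** Let v be its prevalence. With v = 0, 0.40 against 0.20 has power 59.5%.
- A: control = v + (1 − v) × 0.40; Envarsus = v + (1 − v) × 0.20.
- B: later risk i = (0.40 − v)/(1 − v); control = 0.40; Envarsus = v + (1 − v) × i/2.

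| v | A: rates | RR | Power | B: rates | RR | Power |
|---|---|---|---|---|---|---|
| 5% | 0.43 vs 0.24 | 0.56 | 52% | 0.40 vs 0.225 | 0.56 | 47% |
| 10% | 0.46 vs 0.28 | 0.61 | 47% | 0.40 vs 0.25 | 0.63 | 36% |

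**Step 3: does dropping baseline positives restore power?** With no other losses, 47 or 45 per group remain at v = 5 or 10%. Power is then 57 or 56% (A) and 52 or 46% (B), above the Step 2 values. If 20% of controls also lack a baseline urine result at v = 5% (about 37 against 47), power is about 50% (A) and 45% (B). That is below the 52% and 47% without the rule.

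**The case against.** **Section 3.1 already screens both groups.** It requires no prior BK and a negative month 1 screen, and the centre monitors urine as well as serum. A reader might infer from the serum-only wording of 4.1 that any viruria acquired since transplant can be scored. The documents do not support that: 3.1, read naturally, bars viruria known by month 1. What stands is viruria that arises after that screen and is present at Day 0. For controls, prior BK has no reference date, so it is not a stated match for the entry exclusion.

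**New onset is evidently intended.** Sections 1.1 and 12 speak of incidence, and 3.1 of patients who will develop viruria. This shows intent, but no text says which sample starts the count, and the control records already exist when that choice is made. Scoring Day 0 viruria in both groups is conservative for Envarsus; the serum asymmetry is not.

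**Large effects are implausible.** Viruria of 20% at Day 0 would be half the year's expected 40%, reached about four weeks after a negative screen. Month 2 viremia of 10% would exceed the 8% total in 2.3.2. This objection stands, and the illustrations stay below both.

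**Early enrolment shrinks the asymmetry.** This also stands. Step 1 gives the size when everyone enrols near week 8, and the actual distribution is unknown.

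**Conclusion.** The concern holds, with two parts that push in opposite directions. Followed as written, the plan removes entry viremia from the study group only, which biases the primary comparison towards Envarsus. It also lets viruria present at Day 0 count as an outcome, which dilutes any effect if scored in both groups.

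The size cannot be fixed from the documents because neither prevalence is given. Under the stated assumptions, the chance of a false significant result for Envarsus is about 3.0 to 5.2% instead of 2.6%, and power falls from 59.5% to 47–52% (A) or 36–47% (B).

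A reader might infer that the false-positive risk is several times nominal, or that a new-onset rule is sure to raise power. The first needs a month 2 viremia rate above anything that 2.3.2 suggests. The second fails if enough controls lack baseline urine results. The firm gain from correction is that the one-sided bias goes. The change should be made; confidence in the size of the effect is moderate at best.

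**What to change.** Leave enrolment under 4.1 as it is and act on the analysis set.

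- Fix in advance one baseline landmark at the same time since transplant in both groups: month 2, the latest permitted Day 0. State beforehand which sample represents it. Day 0 serves late enrollees. For enrolment at week 4 or 5, Day 30 falls at post-transplant day 58 or 65, close to month 2 (about day 61). Do not choose the control baseline after seeing the study group's timing.
- Apply the serum condition (below 500 copies/mL) at that landmark to controls and study patients alike.
- Define the primary event as the first urine or serum result above 500 copies, or BK nephropathy, after the landmark. Do not count results at or before it.
- Exclude patients already above 500 in urine or serum at the landmark from the primary at-risk set in both groups, and report them separately.
- As sensitivity analyses, show all patients, and a count from Day 0 (study group) and month 1 (controls).
- Reconcile 3.1 with 4.1 on the specimen and threshold of the BK screen, and state the date to which prior BK refers.
- Report the distribution of Day 0 timing and the number of controls without a month 2 urine result.

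**Cost.** The study group needs no new test, since urine and serum PCR are already scheduled. The work is a rewritten endpoint definition and a check of control records. The primary set shrinks by the baseline prevalence, events between conversion and month 2 in early enrollees leave the primary count, and controls without month 2 urine data cannot be classified.
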